#### 3.2 Clinical data

Since the launch of the first BDDE-cross-linked HA dermal filler for aesthetic use in 1996, over 50 clinical studies have been conducted with this type of medical device, which included more than 9,000 subjects. HA gels are currently considered as the gold standard for dermal fillers and are widely used in aesthetic dermatology for facial rejuvenation and re-contouring, with a remarkable track record of performance and safety. Over time, their use was extended to medical reconstructive purposes in the treatment of pathologic conditions like facial lipoatrophy, morphologic asymmetry of the face, and depressed scars. In order to improve the comfort of filler injections, novel formulations containing a local anaesthetic, lidocaine hydrochloride, have been developed to reduce procedural pain and to bypass the need for additional anaesthesia.

Lidocaine hydrochloride is a well-known local anaesthetic, which has been in clinical use for over 60 years. It is currently one of the most widely used local anaesthetics. When used for infiltrative anaesthesia, lidocaine hydrochloride has fast onset of action and moderate duration of effect lasting 1.5-2 h. Absorbed lidocaine is metabolized in the liver and eliminated via the kidneys with a half-life of around 90 minutes. Lidocaine is generally well tolerated and safe. Adverse reactions are rare and usually result from high plasma concentrations due to accidental intravascular injection, excessive dosage (>400 mg), or rapid absorption from highly vascular areas. Early symptoms of toxicity include a metallic taste, tinnitus, light-headedness and confusion, and may be followed by tremors, shivering, seizures and, ultimately, respiratory arrest. Cardiovascular toxicity may be manifested by hypotension, bradycardia, arrhythmia and cardiac arrest.

The performance and safety of HA dermal fillers supplemented with lidocaine hydrochloride have been studied in several randomized clinical trials, which were mostly designed as split face trials, where the same dermal filler was administered with and without ancillary lidocaine. A detailed analysis of nine randomized clinical trials with the equivalent devices **control of the second analysis** of the studies, and present irrespective of the dermal filler tested. The frequency and severity of adverse events (AEs) was not different for dermal fillers with or without lidocaine, indicating no incremental safety risk.

saypha® VOLUME Lidocaine received the European Conformity (CE) mark in March 2016.

A prospective, open label, multicenter, post market study evaluating Princess® VOLUME Lidocaine for the correction of nasolabial folds has been conducted. The results regarding performance endpoints showed that Princess® VOLUME Lidocaine is effective in reducing nasolabial folds. At the primary endpoint (Week 24 assessment) 94.1% of the per-protocol subjects demonstrated ≥1 grade improvement in their nasolabial fold severity compared with the Baseline status. The finding regarding

safety endpoint indicated that Princess® VOLUME Lidocaine is safe and well tolerated. All reported AEs were mild. No serious AEs or deaths were reported in the investigation.

#### 3.3 Justification for the clinical investigation

The current clinical investigation is designed to evaluate the performance of saypha® VOLUME Lidocaine for the correction of nasolabial folds using injection into the deep dermis or supraperiostal and to compare two different manufacturing sites.

In addition, this investigation should support the approval by obtaining clinical data on the performance and safety of saypha® VOLUME Lidocaine for the correction of nasolabial folds.

A prospective, non-comparative design was selected because it allows for the most efficient collection of clinical data on the investigational device, in a manner which is appropriate to address the purpose and objectives of the present investigation. In the absence of spontaneous improvement of nasolabial folds, it is reasonable to assume that the treatment effect can be adequately assessed by comparing the post-treatment observations versus baseline, eliminating the need for a control group. The randomization regarding manufacturing site, C1 and HQ, will be performed according the ratio 1:1 to present the results of the two manufacturing sites descriptively.

The primary performance endpoints are based on evaluation using a validated 5-point scale for assessment of severity of nasolabial folds, the Nasolabial Folds Severity Rating Scale (NLF-SRS), and is set at 24 weeks after administration of the device to address the minimum required durability of effect. Follow-up is extended a maximum up to 104 weeks, to get additional information on long-term effects and to evaluate the aesthetic outcome. Information on occurrence of pain will be primarily obtained by collection of AEs, with additional insight into pain intensity being obtained directly after the injection using a validated 11-point Numeric Pain Rating Scale (NRPS).

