#### 6.1.1 Randomization

Subjects will be randomly assigned to manufacturing site (C1 and HQ) by means of a computergenerated randomization list with a 1:1 allocation. Eligible subjects are assigned random numbers in ascending order within each block beginning with the lowest number available. It is mandatory to stick to this procedure throughout the study.

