#### 7.1 Sample size

Up to approx. 100 + 10 subjects with moderate to severe nasolabial folds will be randomized with a 1:1 allocation to the manufacturing sites C1 and HQ, in order to obtain the 24-week performance and safety data from approximately 50 of them in each manufacturing site. This sample size is considered appropriate for the clinical investigation and sufficient to provide robust estimations on performance and safety parameters in the study population. A sample size of approximately 50 allows a meaningful range estimation, the confidence interval, for the true proportion of success (reduction in NLF-SRS grades of  $\geq$ 1) at week 24. With a sample size of 50, a confidence level of (1-  $\alpha$ ) with  $\alpha$ =0.05 and an estimated proportion of 0.9 a two-sided 95% confidence interval for the true proportion using the large sample normal approximation is given through [0.817; 0.983]. Thus, in compliance with the study design, the true proportion is expected in the range of the confidence interval with an error probability of 5%.

A 'responder' is defined having at least  $\geq$  1 grade improvement as evaluated with the 5 point-validated NLF-SRS at week 24 relative to Baseline (Day 0) score on both sites. Individual NLF-SRS grades per visit will be assessed separately for the right and left NLF. A Response rate of 90% at week 24 is estimated.

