#### 7.4.1 *Performance endpoints*

As two facial folds of each subject will be considered, there are two measurements per subject for NLF-SRS. No great differences between the folds are expected, thus the mean of both measurements will be used for analyses. NLF-SRS grades per visit will be calculated as the mean of grades assigned to

the left and the right nasolabial fold, respectively. The absolute NLF-SRS change versus baseline will be computed by subtracting the value obtained on the corresponding visit from that obtained on Day 0 . Absolute NLF-SRS change from baseline will be summarized by the visit using descriptive statistics and additionally the 95% confidence intervals of the expected change from baseline will be given. In addition, the proportion (with two-sided 95% confidence intervals) of subjects with NLF-SRS improvement (i.e., reduction on both sides in NLF-SRS grades) of  $\geq$ 1, or  $\geq$ 2, respectively, will be calculated.

Individual GAIS grades, subjects' satisfaction with aesthetic outcome, and pain ratings will be summarized and tabulated by visit using descriptive statistics.

Summaries will be provided for the whole analysis population, as well as within each manufacturing site, C1 and HQ, separately.

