This Statistical analysis plan (SAP) is issued to provide a comprehensive and detailed description of strategy, rationale, and statistical technique that will be used to assess the safety and effectiveness of saypha® VOLUME Lidocaine in the correction of moderate-to-severe nasolabial folds (NLFs).

The credibility of the investigation findings will be ensured by pre-specifying the statistical approaches to the analysis of the data prior to results available in this open clinical investigation.

This SAP is based on the clinical investigation plan (CIP) number CPH-101-201477 Version 5.0, dated June 09, 2020.

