1.3 Modifications from the statistical section in the protocol

Not applicable.

2 Investigational plan

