2.1 Design description and randomisation

The present investigation is designed as a prospective, non-comparative, randomized, multicenter study. As justified in the CIP, this type of design is considered appropriate in view of the purpose and objectives of the study.

The investigation will consist of 11 visits (the three last visits are optional): the baseline (Day 0) visit, which will entail informed consent, screening assessments, the treatment, and early post-treatment assessments, telephone communication approximately 24 hours post-administration for monitoring of adverse events and follow-up visits at Week 2, 4, 24, 36, 52, 65 (optional), 78 (optional) and 104 (optional) after the treatment. Procedures to be performed at each visit are specified in section 2.3 Study plan.

In case it is observed by the investigators that at a given visit no aesthetic effect is any more visible in approximately 75 % of the subjects, the study can be terminated at an earlier time point, but not before week 52.

[figure not shown]
Once a subject has consented to enter this study the study participants receive a unique 5-digit number at Day 0, with the first two digits identifying the site and the last three digits identifying the subject, e.g. 01-001. Eligible subjects are assigned to random numbers (starting with 501) in ascending order within each site beginning with the lowest number available. It is mandatory to stick to this procedure throughout the study. Each treated subject will receive test product produced by one of the two manufacturing sites only. The manufacturing sites (C1, HQ) will be assigned to the codes A or B by CROMA.

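### The plan randomises by manufacturing site and speaks of comparing the two, but displays no C1 minus HQ difference or interval: a cheap improvement

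*Protocol*

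**What the plan says.** Protocol 3.3 gives two aims in one sentence: to evaluate performance, and "to compare two different manufacturing sites". The same section then calls the design non-comparative and says the 1:1 randomisation serves "to present the results of the two manufacturing sites descriptively". The objectives in protocol 5.1 name no site comparison. Protocol 5.2 and SAP 3.4.3.1 exclude formal hypothesis testing.

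The planned outputs follow the descriptive reading. Protocol 7.4.1 states: "Summaries will be provided for the whole analysis population, as well as within each manufacturing site, C1 and HQ, separately". SAP 3.4 and 3.4.3.2 have the same layout, with a 95% confidence interval for each response rate and each mean improvement. Neither document specifies a difference between C1 and HQ.

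The sample size text (protocol 7.1, with near-identical wording in SAP 2.2) concerns one site only: "A sample size of approximately 50 allows a meaningful range estimation, the confidence interval, for the true proportion of success". The interval it gives is [0.817; 0.983].

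On masking, the SAP introduction says methods are fixed "prior to results available in this open clinical investigation", and SAP 2.1 says the manufacturing sites "will be assigned to the codes A or B". The primary grade is the investigator's live rating. Protocol 6.4.10 adds grading by an independent blinded photographic reviewer at the end of the study. SAP 3.4.3.2 reports that reviewer's response rate, including Week 24, for the whole population only.

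**The concern.** In a trial randomised by manufacturing site, readers will set the two printed response rates side by side. The planned tables give an interval for each rate but none for the gap. Two separate intervals are easily misread in both directions: a chance gap may look like a site effect, and similar rates may look like evidence that the sites perform alike.

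A reader who wants the contrast must choose a method after seeing the results. The SAP introduction rests the credibility of the findings on pre-specifying the statistical approach. What is at stake is clarity on a purpose that protocol 3.3 itself names. No planned primary or secondary result changes.

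**Working it through.** **Inputs.** From protocol 7.1 and SAP 2.2: about 50 evaluable subjects per site, response rate 0.90, two-sided 95% interval by the large-sample normal approximation. Assumed here: exactly 50 per site and, unless stated otherwise, the same true rate in both.

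**1. The plan's own figure.** 1.96 × √(0.9 × 0.1 / 50) = 0.0832, so 0.9 ± 0.083 = [0.817; 0.983]. This matches.

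**2. The difference, normal approximation (Wald).** 1.96 × √(2 × 0.9 × 0.1 / 50) = 0.1176, or 11.8 points. This is √2 times the one-site half-width. With 55 per site it is 11.2 points.

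**3. The difference, Newcombe.** With d = p1 − p2 and Wilson limits (l, u) for each rate:
- lower limit = d − √((p1 − l1)² + (u2 − p2)²)
- upper limit = d + √((u1 − p1)² + (p2 − l2)²)

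For 45/50 the Wilson limits are 0.786 and 0.957. With 45/50 in both sites, √(0.1136² + 0.0565²) = 0.127, or 12.7 points.

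| Observed | Difference | 95% Newcombe interval |
|---|---|---|
| 45 v 45 | 0 | −12.7 to 12.7 points |
| 47 v 47 (94%, close to the 94.1% in the earlier study in protocol 3.2) | 0 | −10.9 to 10.9 |
| 46 v 44 | 4 | −8.6 to 16.8 |
| 45 v 38 | 14 | −0.9 to 28.6 |
| 45 v 37 | 16 | 0.8 to 30.7 |

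Against 45/50, the interval first excludes zero at 37/50.

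**4. Behaviour over repeated trials.** Summing binomial probabilities over all 51 × 51 outcomes:
- Both true rates 90%: the printed rates differ by 6 points or more in 40.0% of trials and by 10 points or more in 13.1%. The Newcombe interval excludes zero in 3.6%.
- True rates 90% and 80% (assumed): the Newcombe interval excludes zero in 27.0%.

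**5. Choice of method.** For X ~ Binomial(50, 0.9), the planned one-site normal interval contains 0.9 only when X is 40 to 47, which has probability 0.879 rather than 0.95. For the difference the normal method does better: with both true rates 90% it excludes zero in 5.9% of trials. Newcombe is the safer choice, but fixing a method in advance matters more than which one.

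**6. Mean NLF-SRS improvement.** The documents give no standard deviation. The half-width is t(0.975; 98 df) × SD × √(2/50). For an assumed SD of 0.4, 0.6 or 0.8 it is 0.16, 0.24 or 0.32 grade.

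**The case against.** The plan is coherent without this addition. Protocol 3.3 qualifies its own verb: the design is non-comparative and the site results are descriptive. The objectives name no comparison. A reader might infer that a required analysis is missing, or that the plan contradicts itself on its purpose. The documents do not support that; what they contain is one loose verb, qualified in the same section.

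A reader might also infer that the role of chance cannot be judged from the planned tables. That is too strong. SAP 3.4 and 3.4.3.2 provide numbers, percentages, means, standard deviations and per-site intervals, from which an unadjusted difference and interval follow. The gap is in display and pre-specification.

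The gain is also limited. The contrast is imprecise, has no margin to be read against, and uses a live grade in an open study. Randomisation alone does not protect such a grade if the rater knows the assignment. It would still go too far to say that investigators know it: the available text does not say either way, and the sites carry codes. The blinded photographic grade is the natural companion.

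What does not stand is that a non-comparative label rules out the addition. The documents exclude testing, not estimation, and already plan descriptive confidence intervals.

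**Conclusion.** The point holds as a cheap improvement, not as an error. On a purpose that protocol 3.3 names, and for which subjects are randomised, the contrast and its uncertainty are not pre-specified or shown. The only stated precision, 8.3 points, applies to one site; the difference would carry about 11.8 to 12.7 points. This rests on 50 evaluable subjects per site and 90% response in both. At 47/50 in each site the Newcombe half-width is about 11 points.

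The contrast would reveal only large differences. Similar rates would not show that the sites are equivalent: no margin is defined, and even 45/50 in each leaves a true gap of about 12 points open.

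**What to change.** In SAP 3.4.3.2 and protocol 7.4.1 add:

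> In the ITT population, the C1 minus HQ difference at Week 24 will be given descriptively for response rate (two-sided 95% Newcombe confidence interval, used because rates near 90% with 50 subjects per site make the normal approximation poor) and for mean NLF-SRS improvement (two-sided 95% confidence interval). No test is done, and no equivalence conclusion follows because no margin is defined. The same response-rate difference will be given for the Week 24 grade of the independent blinded photographic reviewer.

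Further edits:
- In protocol 7.1 and SAP 2.2, state the expected precision of the difference: about ±12 to 13 points at 50 per site and 90% response.
- In protocol 3.3, replace the comparison clause with: describe the results of the two manufacturing sites and the difference between them.
- If only the SAP changes, list the addition in SAP 1.3, which now records no modification.
- For the photographic contrast, allow an exception to SAP 3.4, which limits exploratory analyses to the whole population. Confirm Week 24 as a photographic visit: protocol 6.1.4 and SAP 3.4.3.2 include it, but the protocol synopsis and SAP 1.2.3 do not. Because the blinded grading takes place at the end of the study, this contrast belongs in the final analysis.

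Adverse event tables stay as planned. The cost is a few table rows, a sentence on precision and a reworded clause, with no extra subjects and no change to any planned result. The downside is an imprecise contrast that could be over-read without its descriptive label.

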### 4 Risks and benefits of the investigational device and clinical investigation

#### 4.1 Anticipated clinical benefits

The treatment with saypha® VOLUME Lidocaine may remove or reduce a distressing aesthetic defect in subjects with moderate-to-severe nasolabial folds, thereby improving their psychological and social wellbeing. This is achieved by a minimally invasive procedure with a short downtime, which results in an immediate and long-lasting effect, persisting for 6-12 months.

#### 4.2 Anticipated adverse device effects

The safety profile of BDDE-cross-linked HA dermal fillers, with or without lidocaine, is well established. In general, these devices are well tolerated and safe, with a low frequency of side effects. Adverse effects that have been observed with devices similar to saypha® VOLUME Lidocaine are summarized in Table 2, on the following page.

"A prospective, open label, multicenter, post market study evaluating Princess® VOLUME Lidocaine for the correction of nasolabial folds" all 62 screened and enrolled subjects were treated with the investigational medical device at Baseline. The mean number of used devices was 2.7 (standard deviation [SD]: 0.8) and the mean injected volume was 1.15 mL (SD: 0.46) for the right nasolabial folds, and 1.16 mL (SD: 0.45) for the left nasolabial folds. At Week 2, eight subjects received touch-up treatment using a mean of 1.1 mL (SD: 0.4) investigational medical devices. The mean injected volume for touch-up treatment was 0.45 mL (SD: 0.3) for the right nasolabial folds, and 0.29 mL (SD: 0.3) for the left nasolabial folds. The results show that adverse device effects include injection site hematoma, hypoesthesia and pain, one subject showed nervous system disorder and one subject had syncope. However, all ADEs were mild and had resolved within a maximum of 13 days of their onset.

Table 2. Adverse effects of cross-linked hyaluronic acid dermal fillers (with or without lidocaine)

Common	Rare	Very rare

 
Redness, erythema
 
Swelling, oedema
 
Pain, itching, burning, discomfort
 
Tenderness
 
Bleeding
 
Bruising, hematoma
 
	
 
Hypersensitivity, angioedema
 
Infection, abscess
 
Herpes reactivation
 
Irritation, inflammation, granuloma
 
Malar oedema
 
Implant visibility, nodules, beading, lumpiness, implant-site mass
 
Firmness, induration
 
Discoloration, dispigmentation, puncture marks
 
Paresthesia, numbness
 
Implant migration
 
Scar sarcoidosis
 
Scleromyxedema
 
Teleangiectasia (generalized)
 
Vasculitis cutaneous
 
Vasospasm
 
Vasovagal reaction during injection
 
	
 
Vascular compromise or arterial occlusion (typically presented as immediate skin blanching, followed by a Livedoid pattern, discoloration or necrosis)
 
Retinal artery occlusion, vision loss
 
Necrosis
 

Common AEs like swelling, redness, tenderness, pain and bruising are typically mild in severity and usually resolve within 1-2 days after injection; resolution of bruising may take a little bit longer. Discomfort and pain may be reduced or prevented by application of ice before the injection. Redness, swelling and bruising may be prevented or alleviated by application of ice-packs for 5-10 minutes after the injection.

Additional information on AEs, especially serious events like arterial occlusion and necrosis is provided in the IB.

In case impending tissue necrosis, which may occur with any dermal filler, a recent consensus statement on the treatment of HA filler-induced impending necrosis recommends immediate treatment with high doses of hyaluronidase (e.g., at least 200 units of Vitrase®, or equivalent), followed by warm compress, vigorous massage and topical nitroglycerin paste. If no improvement is seen within 60 minutes, additional quantities of hyaluronidase should be injected (3-4 cycles in total). An oral aspirin regimen (e.g., 650 mg per day) should help prevent further clot formation. Daily follow-up is advised.

In case of an adverse event the Expert Consensus Recommendations for treatment of Soft Tissue Filler Complicationsshould be followed in the discretion of the investigator. The current Expert Consensus Recommendations for treatment of Soft Tissue Filler Complication are filed in the Investigator's File.

#### 4.3 Possible interactions with concomitant medical treatments

No studies on drug interactions with saypha® VOLUME Lidocaine have been conducted in humans.

Anticoagulant and antiplatelet drugs may increase the risk of bleeding or bruising, so the subject should be asked about use of such medications, and the prescribing physician should be consulted to appropriately assess the risk level.

Sodium hyaluronate is incompatible with quaternary ammonium compounds such as benzalkonium chloride solutions. The device should never be placed in contact with these substances or with medical-surgical instruments that have been in contact with these substances.

#### 4.4 Risk mitigation strategy

The risks will be mitigated by careful selection of the subjects and exclusion of those who may have an increased risk of developing certain types of AEs (see Section 6.3.5), proper injection technique (described in Section 6.2.2), appropriate training of the investigators to ensure correct application of the device, and regular follow-up visits over the following 104 weeks (maximum), which will allow for timely recognition and management of potential AEs. After insertion of the needle / cannula, and just before injection, the plunger rod should be withdrawn slightly to aspirate and verify that the needle is not intravascular. Furthermore, the subjects will be instructed to immediately contact the investigator in case of occurrence of any AE between the scheduled visits.

